### 3.2 Post Study Access to Therapy

At the end of the trial (6 months) patients will be treated according to local standards of care.

Patients will be contacted by telephone 30 days +/- 7 days after the end of treatment study visit for additional follow-up. At this contact, bleeding, death/ischemic events, antithrombotic therapy and INR values will be assessed.

At the end of the study, BMS will not continue to provide BMS supplied study drug to subjects/investigators unless BMS chooses to extend the study. The investigator should ensure that the subject receives appropriate standard of care to treat the condition under study.

As the oral anticoagulant is not blinded, investigators will be free to choose at the end of the study whether to continue the apixaban or VKA, or transition to alternative agents. Patients transitioning from apixaban to vitamin K antagonists should have frequent INR tests during the first few weeks of transition, as per local standards. Furthermore, investigators will not be routinely provided blinded aspirin/aspirin placebo assignments until after the final study results are made public.

### **3.3 Study Population**

For entry into the study, the following criteria **MUST** be met.

#### **3.3.1 Inclusion Criteria**

##### **1. Signed Written Informed Consent**

- a) Subjects will be required to provide a written informed consent.

##### **2. Target Population**

- a) Males and females 18 years of age (or age of majority) or older with either active or a history of non-valvular atrial fibrillation or flutter with the planned or existing use of an oral anticoagulant for prophylaxis of thromboembolism for at least 6 months **AND**
- b) An acute coronary syndrome (ST-elevation myocardial infarction [STEMI], non-ST-elevation myocardial infarction [NSTEMI], or unstable angina), within the prior 14 days, with planned use of an approved P2Y12 inhibitor for at least 6 months **AND/OR**
- c) PCI (with or without stents) within the prior 14 days with planned use of an approved P2Y12 inhibitor for at least 6 months.

**(If both an ACS event and an elective PCI occur within the same 14 day period, the investigator has the option to define the index event for the randomization to the interactive voice/web response system. It is recommended to choose the most recent event as the index event. However, for the electronic case report form, if a patient has both an ACS and PCI within 14 days, both events can be selected.)**

##### **3. Subject Re-enrollment:**

- a) This study does permit the re-enrollment of a subject that has discontinued the study as a pre-treatment failure (screen failure).

#### 4. Age and Reproductive Status

- a) Women of childbearing potential (WOCBP) must have a negative serum or urine pregnancy test (minimum sensitivity 25 IU/L or equivalent units of HCG) within 24 hours prior to the start of study drug.
- b) Women must not be breastfeeding
- c) WOCBP must agree to use effective contraception for the duration of treatment with study drugs plus
  - i. 33 days for patients on apixaban
  - ii. 40 days for patients on VKA
- d) Azoospermic males and WOCBP who are continuously not heterosexually active are exempt from contraceptive requirements. However they must still undergo pregnancy testing as described in this section.

Investigators shall counsel WOCBP and male subjects who are sexually active with WOCBP on the importance of pregnancy prevention and the implications of an unexpected pregnancy. Investigators shall advise WOCBP and male subjects who are sexually active with WOCBP on the use of highly effective methods of contraception. Highly effective methods of contraception have a failure rate of < 1% when used consistently and correctly. In addition, subjects and their partners should utilize two methods of contraception, such as a barrier method and hormonal method, especially for subjects randomized to VKA.

#### 3.3.2 Exclusion Criteria

##### 1. Target Disease Exceptions

- a) Conditions other than non-valvular atrial fibrillation that require chronic anticoagulation (eg, mechanical heart valve)

##### 2. Medical History and Concurrent Diseases

- a) Severe renal insufficiency (serum creatinine > 2.5 mg/dL [221 micromol/L] or a calculated creatinine clearance < 30 mL/min)
- b) Patients with any history of intracranial hemorrhage
- c) Any contraindications to VKA, apixaban, or to intended P2Y12 antagonists or to aspirin
- d) Patients who have or will undergo coronary arterial bypass graft (CABG) for their index ACS event
- e) Women who are pregnant, breastfeeding, or of childbearing potential and unable to use an acceptable method of birth control

##### 3. Physical and Laboratory Test Findings

- a) Patients with known ongoing bleeding
- b) Patients with known coagulopathies

#### **4. Allergies and Adverse Drug Reaction**

- a) Known allergies or sensitivities to apixaban, VKA, aspirin, or to intended P2Y12 antagonist.

#### **5. Other Exclusion Criteria**

- a) Prisoners or subjects who are involuntarily incarcerated
- b) Subjects who are compulsorily detained for treatment of either a psychiatric or physical (eg, infectious disease) illness
- c) Subjects who would have compromised ability to comply with study therapy or follow up visits
- d) Subjects who are participating in other interventional clinical trials of other drugs or unapproved devices.

#### **6. Current employees of Pfizer, Bristol-Myers Squibb, or PPD are excluded from participation, as well as their spouses and dependent children.**

Eligibility criteria for this study have been carefully considered to ensure the safety of the study subjects and that the results of the study can be used. It is imperative that subjects fully meet all inclusion criteria and no exclusion criteria.

#### **3.3.3 Women of Childbearing Potential**

A Women of childbearing potential (WOCBP) is defined as any female who has experienced menarche and who has not undergone surgical sterilization (hysterectomy or bilateral oophorectomy) and is not postmenopausal. Menopause is defined as 12 months of amenorrhea in a woman over age 45 years in the absence of other biological or physiological causes. In addition, females under the age of 55 years must have a serum follicle stimulating hormone, (FSH) level > 40mIU/mL to confirm menopause.

Females treated with hormone replacement therapy, (HRT) are likely to have artificially suppressed FSH levels and may require a washout period in order to obtain a physiologic FSH level. The duration of the washout period is a function of the type of HRT used. The duration of the washout period below are suggested guidelines and the investigators should use their judgement in checking serum FSH levels. If the serum FSH level is > 40 mIU/ml at any time during the washout period, the woman can be considered postmenopausal:

- 1 week minimum for vaginal hormonal products (rings, creams, gels)
- 4 week minimum for transdermal products
- 8 week minimum for oral products

Other parenteral products may require washout periods as long as 6 months.

### **3.4 Concomitant Treatments**

#### **3.4.1 Prohibited and/or Restricted Treatments**

During the 6 month treatment period, oral or parenteral anticoagulants (excluding low molecular weight heparins (LMWH or unfractionated heparins (UFH) for the purpose of bridging to VKA treatment only), including the novel oral anticoagulants (excluding apixaban for those assigned to that arm), as well as non-study aspirin, may not be given concurrently. However, transition from pre-randomization medications, such as bridging heparin, may be given at the discretion of the investigator, to overlap with study treatments.

#### **3.4.2 Pre-Randomization Concomitant Medication**

All concomitant medications from 7 days before randomization to end of study should be recorded in the electronic case report form.

### **3.5 Discontinuation of Subjects following any Treatment with Study Drug**

Subjects MUST discontinue investigational product (and non-investigational product at the discretion of the investigator) for any of the following reasons:

- Subject's request to stop study treatment
- Any clinical adverse event (AE), laboratory abnormality or intercurrent illness which, in the opinion of the investigator, indicates that continued participation in the study is not in the best interest of the subject
- Termination of the study by Bristol-Myers Squibb (BMS)
- Loss of ability to freely provide consent through imprisonment or involuntarily incarceration for treatment of either a psychiatric or physical (eg, infectious disease) illness.

In the case of pregnancy, the investigator must immediately notify the BMS Medical Monitor/designee of this event. In most cases, the study drug will be permanently discontinued in an appropriate manner. If the investigator determines a possible favorable benefit/risk ratio that warrants continuation of study drug, a discussion between the investigator and the BMS Medical Monitor/designee must occur.

All subjects who discontinue study drug will be contacted by telephone 30 days +/- 7 days after the end of study visit as detailed in [Section 3.2](#) and [Table 5.1-2](#). The only exception to this requirement is when a subject withdraws consent for all study procedures including post-treatment study follow-up or loses the ability to consent freely (ie, is imprisoned or involuntarily incarcerated for the treatment of either a psychiatric or physical illness).

If study drug is discontinued prior to the subject's completion of the study, the reason for the discontinuation must be documented in the subject's medical records and entered on the appropriate case report form (CRF) page.

### **3.6 Post Study Drug Study Follow up**

In this study, bleeding is a key endpoint of the study. Post study follow-up is of critical importance and is essential to preserving subject safety and the integrity of the study. Subjects

who discontinue study drug must continue to be followed for collection of outcome and/or survival follow-up data as required and in line with [Section 5](#) until death or the conclusion of the study.

### **3.6.1 Withdrawal of Consent**

Subjects who request to discontinue study drug will remain in the study and must continue to be followed for protocol specified follow-up procedures. The only exception to this is when a subject specifically withdraws consent for any further contact with him/her or persons previously authorized by subject to provide this information. Subjects should notify the investigator of the decision to withdraw consent from future follow-up **in writing**, whenever possible. The withdrawal of consent should be explained in detail in the medical records by the investigator, as to whether the withdrawal is from further treatment with study drug only or also from study procedures and/or post treatment study follow-up, and entered on the appropriate CRF page. In the event that vital status (whether the subject is alive or dead) is being measured, publicly available information should be used to determine vital status only as appropriately directed in accordance with local law.

### **3.6.2 Lost to Follow-Up**

All reasonable efforts must be made to locate subjects to determine and report their ongoing status. This includes follow-up with persons authorized by the subject as noted above. Lost to follow-up is defined by the inability to reach the subject after a minimum of three documented phone calls, faxes, or emails as well as lack of response by subject to one registered mail letter. All attempts should be documented in the subject's medical records. If it is determined that the subject has died, the site will use permissible local methods to obtain the date and cause of death.

If investigator's use of third-party representative to assist in the follow-up portion of the study has been included in the subject's informed consent, then the investigator may use a Sponsor-retained third-party representative to assist site staff with obtaining subject's contact information or other public vital status data necessary to complete the follow-up portion of the study. The site staff and representative will consult publicly available sources, such as public health registries and databases, in order to obtain updated contact information. If after all attempts, the subject remains lost to follow-up, then the last known alive date as determined by the investigator should be reported and documented in the subject's medical records.

Even after multiple unsuccessful contact attempts, no subject should be considered truly lost to follow-up until the final conclusion of the CV185316 study, as subjects may unexpectedly present themselves well after their scheduled final visit.

## **4 STUDY DRUG**

Study drug includes both Investigational [Medicinal] Product (IP/IMP) and Non-investigational [Medicinal] Product (Non-IP/Non-IMP) and can consist of the following:

**Table 4-1: BMS Supplied Study Drugs for CV185316**

Product Description / Class and Dosage Form	Potency	IP/ Non-IMP	Blinded or Open Label	Packaging/ Appearance	Storage Conditions (per label)
Acetylsalicylic acid film coated tablet	81 mg	IP	blinded	35 tablets/bottle White to off white, plain, round, biconvex film coated tablet	Store at 15-25°C (59-77°F). Store in a tightly closed container.
Placebo for Acetylsalicylic acid film coated tablet	0 mg	IP	blinded	35 tablets/bottle White to off white, plain, round, biconvex film coated tablet	Store at 15-25°C (59-77°F). Store in a tightly closed container.
Apixaban film coated tablet a	2.5 mg	IP	Open Label	30 tablets/blister wallet, yellow, round, biconvex film coated tablets with “893” debossed on one side and “2 1/2” on the other side.	Store at 15-25°C (59-77°F)
Apixaban film coated tablet a	5 mg	IP	Open Label	56 tablets/blister wallet, Pink, oval shaped, biconvex film coated tablets with “894” debossed on one side and “5” on the other side.	Store at 15-25°C (59-77°F)
Warfarin tablets a	1 mg	IP	Open Label	40 tablets/blister wallet, Pink tablets with a groove on one side and “1” on the other side.	Store at 15-25°C (59-77°F) Protect from light.
Warfarin tablets a	5 mg	IP	Open Label	40 tablets/blister wallet, Yellow tablets with a groove on one side and a “5” on the other side.	Store at 15-25°C (59-77°F) Protect from light.

a Supplied in countries where local sourcing is not permissible.

Apixaban 5 mg and 2.5 mg tablets, as well as VKA and the P2Y12 inhibitors used will be locally sourced materials (to be purchased by the sites through local commercial sources) wherever possible and not supplied by Bristol-Myers Squibb. Apixaban 5 mg and 2.5 mg tablets as well as Warfarin 1 mg and 5 mg tablets listed in Table 4-1 will be supplied in countries where local sourcing is not an option.

Locally sourced material should be kept at appropriate storage conditions in accordance with the package insert. BMS considers the blinded aspirin and blinded aspirin placebo to be Investigative Product (IP) as well as the apixaban and VKA; the P2Y12 inhibitors are considered to be non-IP study medications. For this study, apixaban/VKA and aspirin/aspirin-placebo are considered “study drugs;” the required P2Y12 inhibitors are considered background medications.

#### **4.1 Investigational Product**

An investigational product, also known as investigational medicinal product in some regions, is defined as a pharmaceutical form of an active substance or placebo being tested or used as a reference in a clinical study, including products already with a marketing authorization but used or assembled (formulated or packaged) differently than the authorized form, or used for an unauthorized indication, or when used to gain further information about the authorized form.

The investigational product should be stored in a secure area according to local regulations. It is the responsibility of the investigator to ensure that investigational product is only dispensed to study subjects. The investigational product must be dispensed only from official study sites by authorized personnel according to local regulations. In this study, apixaban 2.5 mg and 5 mg tablets, as well as the aspirin 81 mg tablets, aspirin placebo, and VKA are considered investigational product.

#### **4.2 Non-investigational Product**

Other medications used as support or escape medication for preventative, diagnostic, or therapeutic reasons, as components of the standard of care for a given diagnosis, may be considered as non-investigational products. In this study, the required P2Y12 inhibitor (eg, clopidogrel) is considered non-investigational product.

#### **4.3 Storage of Study Drug**

The product storage manager should ensure that the study drug is stored in accordance with the environmental conditions (temperature, light, and humidity) as determined by BMS. If concerns regarding the quality or appearance of the study drug arise, the study drug should not be dispensed and contact BMS immediately.

Study drug not supplied by BMS will be stored in accordance with the package insert.

Please refer to [Section 9.2.2](#) for guidance on IP records and documentation.

#### **4.4 Method of Assigning Subject Identification**

At the time of enrollment, each subject will be assigned a unique sequential subject number by IVRS. The IVRS will be available 24 hours per day, seven days a week. The subject number will consist of a unique 5 digit number which is assigned sequentially within a study (starting with 00001) by the IVRS. This number will be used for identification throughout the study and will not be used for any other subject.

Each subject who meets the inclusion/exclusion criteria will be randomly assigned to one of the two open label treatment groups: apixaban or VKA, with each treatment arm having an allocation probability of a half (0.50). At the same time, subjects will be randomly assigned in a blinded fashion to aspirin or matching placebo.

The randomization will be stratified by indication at enrollment (PCI/ACS).

#### 4.5 Selection and Timing of Dose for Each Subject

Subjects randomized to apixaban will be dosed at 5 mg bid, unless they meet at least two of the following criteria for dose reduction to 2.5 mg BID:

- Age  $\geq$  80 years
- Weight  $\leq$  60 kg
- Serum creatinine  $\geq$  1.5 mg/dL (133 micromol/L)

Subjects randomized to apixaban may have their dosages increased or decreased during the 6 month treatment period if at least two of the three above criteria change during the study.

Subjects randomized to VKA should be titrated up for an INR target goal of 2.0 to 3.0. Dosages of VKA to achieve that range should be per local standards of care and per investigator clinical judgment.

Both the oral anticoagulant (apixaban or VKA) and the antiplatelet agents (blinded aspirin once daily or blinded placebo once daily) must be started within 24 hours of randomization.

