## 5 STUDY ASSESSMENTS AND PROCEDURES

### 5.1 Flow Chart/Time and Events Schedule

**Table 5.1-1: Baseline and Randomization (CV185316)**

Procedure	Screening/ Randomization Visit	Notes
Eligibility Assessments		
Informed Consent	X	
Inclusion/Exclusion Criteria	X	
Medical History	X	Include assessment of alcohol use, tobacco use, prior VKA use, and CHADS-VASC and HAS-BLED scores
Safety Assessments		
Physical Examination	See Notes	Only if deemed necessary by treating physician. Results of examination will be documented in patient's chart, not on CRF
Vital Signs	X	Blood Pressure and Weight
Assessment of Signs and Symptoms	See Notes	Only if deemed necessary by treating physician. Results of assessment will be documented in patient's chart, not on CRF
Serious Adverse Events Assessment	See Notes	Refer to section 6.1 of the protocol for SAE definitions applying to this study.
Adverse Events Assessment	N/A	
Laboratory Tests	X	Local lab: CBC, chemistry(CHEM7 or equivalent for determination of serum creatinine), coagulation (for PT/PTT/INR) (local lab within 7 days can be used)
Urine Pregnancy Test* ( WOCBP only )	X	*If applicable Serum pregnancy test to be performed only if urine test is positive or un-interpretable
Study Drug		
Randomize	X	
Dispense Study Drug (administer within 24 hours of randomization)	X	Those supplied by BMS or sourced by the investigator

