7.6.1.3 Subgroup Analyses

All analyses described in this section will be performed on the Treated Population for oral anticoagulant during treatment period using the safety censoring scheme.

Table 7.6.1.3 shows the subgroups of interest for analyses of primary safety assessment. If the value of the grouping variable cannot be determined for a subject, the subject will be excluded from the corresponding subgroup analysis. For each subpopulation analysis, if, in any treatment group, the number of events is ≤ 10 for a subgroup, then the grouping variable will not be included in the test of treatment by subpopulation interaction.

Table 7.6.1.3: Subgroups of Interest for Primary Safety Assessments

Grouping Variable	Subgroups
indication at enrollment	PCI ACS
Apixaban dose*	2.5 mg BID 5 mg BID
Geographic region	North America Latin America Europe

Table 7.6.1.3: Subgroups of Interest for Primary Safety Assessments

Grouping Variable	Subgroups
	Asia/Pacific
Age	< 65 years old ≥65 to < 80 years old ≥ 80 years old
Gender	Male Female
Race	White Black / African American Asian Other
Ethnicity (for US only)	Hispanic/Latino Not Hispanic/Latino
Weight	≤ 60 kg > 60 kg
Serum Creatinine	< 1.5 mg/dL ≥1.5 mg/dL
CHADS2 Score	≤ 1 2 ≥ 3
CHADSVASC2 scores	Low (0[male] or 1 [female]) Moderate (1 [male]) High (≥ 2)
HASBLED score	≤ 1 2 ≥ 3
Diabetes Mellitus	Yes No
Hypertension requiring pharmacological treatment	Yes No
Heart Failure	Yes No
Concomitant med (which P2Y12 agent was the subject on)	Clopidogrel Prasugrel Ticlodipine Ticagrelor
Prior warfarin/VKA status at least 2 months prior to the study	Experienced Naive
Antiplatelet	Aspirin

Table 7.6.1.3: Subgroups of Interest for Primary Safety Assessments

Grouping Variable	Subgroups
	Aspirin placebo

*the control for apixaban 2.5 mg will be subjects in the VKA group who meet criteria of apixaban dose adjustment (see section 1); other VKA subjects will be the control for the subjects taking apixaban 5 mg.

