7.6.2.1 Primary Safety Analysis

The primary safety endpoint will be time to first occurrence of confirmed ISTH major or CRNM bleeding. A point estimate and two-sided 95% CIs for hazard ratio using a Cox proportional hazards model including antiplatelet (aspirin/placebo) as a covariate, stratified by indication at enrollment (PCI/ACS) and oral anticoagulant treatment group (apixaban/VKA) using the treated subjects for antiplatelet during treatment period. A p-value for the test of equality (HR = 1) will be calculated based on the hierarchical testing strategy.

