Each of these subgroups will be analyzed using a Cox proportional hazards model stratified by indication at enrollment (not applicable for the first subgroup listed) and oral anticoagulant treatment group (apixaban/VKA) (not applicable for the last subgroup listed) with terms for treatment group. The estimated HR and two-sided 95% CIs will be calculated to assess the treatment effect within each of the subgroups. The p-value for the test of the treatment by grouping variable interaction will be presented based on a Cox proportional hazards model stratified by indication at enrollment (not applicable for the first subgroup listed) and oral anticoagulant treatment group (apixaban/VKA) (not applicable for the last subgroup listed) with terms for treatment group, and the grouping variable and treatment by grouping variable interaction.

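### The apixaban dose subgroup sorts apixaban subjects by dose but VKA subjects by criteria met, and Protocol 4.5 ties in-study dose changes to criteria that change, not criteria met

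*Protocol*

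**What the plan says.** **SAP, Table 7.6.1.3.** One row is apixaban dose, with levels 2.5 mg BID and 5 mg BID. VKA subjects have no apixaban dose, so a footnote assigns them: "the control for apixaban 2.5 mg will be subjects in the VKA group who meet criteria of apixaban dose adjustment", and "other VKA subjects will be the control for the subjects taking apixaban 5 mg". SAP 7.6.1.3 asks for a hazard ratio and 95% CI within each level. It also asks for an interaction p-value, unless a level has 10 or fewer events in either treatment group. The analysis uses the Treated Population for oral anticoagulant.

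Neither the row nor the footnote says when dose or criteria are read. SAP 7.3.1.1 lists apixaban dose at randomization as a baseline characteristic, but the subgroup row does not carry that qualifier. The footnote points to SAP Section 1, which is not in the copy reviewed and may supply a time point. Nothing here rests on its absence.

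**SAP, Table 7.6.2.2.** The footnote is repeated for the aspirin comparison. The contrast there is already set: SAP 7.6.2.1 fits a Cox model "including antiplatelet (aspirin/placebo) as a covariate", and the subgroup models are stratified by anticoagulant.

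**Protocol 4.5.** Apixaban is given at 5 mg BID "unless they meet at least two of the following criteria for dose reduction to 2.5 mg BID". The criteria are age 80 years or more, weight 60 kg or less, and serum creatinine 1.5 mg/dL or more. The next sentence says that apixaban subjects "may have their dosages increased or decreased during the 6 month treatment period", on the condition "if at least two of the three above criteria change during the study".

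**The concern.** A subgroup keeps the protection of randomization when membership is decided by the same baseline facts in both arms. Here one arm is sorted by a treatment variable and the other by subject characteristics. The characteristics mark subjects for whom a lower dose is thought appropriate, so groups that differ on them may differ in bleeding risk. If the sortings diverge, the hazard ratio within a dose level and the interaction p-value mix a treatment difference with a difference in who was included.

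The protocol sentence raises a separate and smaller issue. The starting rule counts criteria met and the in-study rule counts criteria that change. In a bleeding trial, two adjacent sentences that can give different doses for the same subject are worth reconciling.

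**Working it through.** The plan states no event count, power or effect size for this subgroup, so there is no figure of its own to reproduce.

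**Step 1. Compare the two sortings (SAP Table 7.6.1.3 footnote).**

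| Criteria met by apixaban subject | Dose taken | Apixaban subject's level | Level holding VKA subjects with the same criteria | Agree? |
|---|---|---|---|---|
| at least two | 2.5 mg | 2.5 mg | 2.5 mg | yes |
| at least two | 5 mg | 5 mg | 2.5 mg | no |
| fewer than two | 5 mg | 5 mg | 5 mg | yes |
| fewer than two | 2.5 mg | 2.5 mg | 5 mg | no |

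**Step 2. What decides the size.** Let p be the share of subjects meeting at least two criteria, u the share of those in the apixaban arm who are on 5 mg, and v the share of the remaining apixaban subjects who are on 2.5 mg.

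- Apixaban 2.5 mg level: share that does not meet the criteria = v(1−p) / [p(1−u) + v(1−p)]. The VKA control has none.
- Apixaban 5 mg level: share that meets the criteria = up / [up + (1−v)(1−p)]. The VKA control has none.

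Both are zero when u = v = 0. The documents give none of p, u or v, so no number can be put in.

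**Step 3. How u or v could exceed zero.**

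- *Starting dose off criteria.* This would breach Protocol 4.5, but the subject stays in the analysis. SAP 7.2 counts as a treatment error only receipt of the other anticoagulant, whatever the apixaban dose, and that exclusion applies to the Evaluable Population, not the Treated Population.
- *Dose change in the study*, unless dose at randomization is what the row means. Protocol 4.5 permits such changes. Protocol Table 5.1-2 schedules weight at Visits 1 to 3 but no creatinine after baseline, so VKA subjects' status can be read systematically only at baseline, whereas apixaban dose can move later.

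**Step 4. Aspirin table.** Within each anticoagulant arm, aspirin and placebo subjects are sorted by the same rule, and the models are stratified by anticoagulant. The aspirin-versus-placebo contrast therefore stands, and only the definition of membership differs between arms.

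**Step 5. Protocol 4.5, sentence against sentence.** Code each criterion as met or not met, with age unable to revert. The indicated dose changes when the count met crosses two. The literal in-study rule applies when at least two criteria change.

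- Possible changes: age status fixed, 2 × (4×4 − 4) = 24; age newly met, 4×4 = 16; total 40.
- Crossing the threshold: 6 (age not met) + 6 (age met throughout) + 10 (age newly met) = 22.
- Crossing on one criterion only, so not covered: 4 + 4 + 2 = 10 (6 reach two, 4 fall below two). Covered: 22 − 10 = 12.
- Single-criterion changes in all: 8 + 8 + 4 = 20, so 40 − 20 = 20 involve two or more. Of these, 20 − 12 = 8 leave the indicated dose unchanged yet satisfy the literal rule.

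Not covered: age 81, creatinine 1.0 mg/dL, weight 62 to 58 kg (one criterion changed, two now met). Permitted without need: age 70, weight 58 to 62 kg, creatinine 1.3 to 1.6 mg/dL (two changed, one met before and after).

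**The case against.** **On the subgroup.** If the row means dose at randomization, in-study changes drop out and only off-criteria starting doses remain, which the protocol already forbids. This is one of 18 rows in Table 7.6.1.3 and carries no alpha. Sorting by criteria also changes the question from dose received to eligibility for reduction. These points stand as limits on the consequence. They do not make the two arms' definitions the same. Fixing the time point alone would still leave an off-criteria starter facing the wrong controls, and a question about dose received has no randomized counterpart in the VKA arm.

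**On the dosing sentence.** The first sentence of 4.5 is mandatory and has no time limit, so a subject who newly meets two criteria can be read as covered by it. The second is permissive and forbids nothing. The intent is very probably two-of-three status. All of this stands and reduces the point to a wording conflict.

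**Stronger readings that a reader might infer.**

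- That the like-for-like comparison is broken, mainly at 2.5 mg. The documents show only that it would fail under off-criteria dosing or dose changes, and they give nothing to rank the two levels.
- That 10 + 8 = 18 of 40 is an error rate. These are logical states with no patient weights. All 8 needless permissions require one criterion gained and another lost within six months.
- That sites left subjects on too high a dose. Nothing in the documents shows this.

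**Conclusion.** The point holds as a minor correction. The subgroup definition differs between the anticoagulant arms. It gives a like-for-like comparison only if every apixaban subject is dosed to criteria and, unless dose at randomization is intended, stays on that dose. If either condition fails, the hazard ratio within a dose level and the interaction test in Table 7.6.1.3 can be biased, by an amount that the documents do not let us estimate.

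The Protocol 4.5 sentence is secondary. Read literally, it does not cover a single-criterion change that brings a subject to two criteria met or takes the subject below two, although the preceding sentence can be read to do so.

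The primary non-inferiority and superiority tests, the power and the alpha are unaffected, because SAP 6.2 groups subjects by anticoagulant and not by dose.

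**What to change.** **SAP, Table 7.6.1.3.** Rename the row *Dose-reduction criteria at randomization (at least two met / fewer than two met)*. Replace the footnote with: *Defined in both anticoagulant arms from age, weight and serum creatinine at randomization, regardless of dose taken.* A summary by dose actually taken can be kept as descriptive.

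**SAP, Table 7.6.2.2.** Use the same row and footnote, and leave the aspirin-versus-placebo contrast as it is.

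Cost: one row label and one footnote in two tables, with no new data. Protocol Table 5.1-1 collects weight and "CHEM7 or equivalent for determination of serum creatinine" at screening for every subject.

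**Protocol 4.5.** Replace the in-study sentence with: *The dose should be changed to 2.5 mg BID if the subject newly meets at least two of the three criteria, and to 5 mg BID if the subject no longer meets at least two.* Using *should* instead of *may* matters, because a permissive sentence would still allow a subject meeting two criteria to stay on 5 mg.

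Cost: one sentence. Under Protocol 9.1.1 it needs IRB/IEC approval, or notification if done by administrative letter, across about 690 sites (Protocol 3.1). Its reach is limited. SAP 7.9 reports the review at 50% completion as already done, so only subjects still on treatment would benefit. Creatinine-driven changes would still surface only through routine care, because no creatinine is scheduled after baseline. If the treatment period is over, the SAP edit stands on its own.
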